7. ADVERSE EVENTS

7.1. Definition of Adverse Event

Since this is a post-market study and the device is used within its intended use, participation in the study presents minimal risk to the patient. Additionally, this patient population may have numerous comorbidities and health issues unrelated to the wound. Therefore, a narrower definition of a nonserious adverse event (AE) will be used. In this study, an AE is any untoward medical occurrence related to the wound or treatment of the wound, including infection, significant increases in pain, and unexpected reactions at the site of wound device placement.

7.2. Definition of Serious Adverse Event

The FDA definition of a serious adverse event (SAE) will be used in this study: An AE or suspected adverse reaction is considered "serious" if, in the view of either the site investigator or sponsor, it results in any of the following outcomes:

- Death
- A life-threatening adverse event
- Inpatient hospitalization or prolongation of existing hospitalization
- A persistent or significant incapacity or substantial disruption of the ability to conduct normal life functions or,
- A congenital anomaly/birth defect.

Important medical events that may not result in death, be life-threatening, or require hospitalization may be considered serious when, based upon appropriate medical judgment, they may jeopardize the participant and may require medical or surgical intervention to prevent one of the outcomes listed in this definition. All SAEs will be reported to the sponsor, regardless of potential relationship to the wound or treatment of the wound.

7.3. Severity of Adverse Event

The severity of all adverse events will be graded on a scale of one through five according to the Common Terminology Criteria for Adverse Events guideline, where each grade represents a unique clinical description based on this general guideline:

- **Grade 1:** Mild; asymptomatic or mild symptoms; clinical or diagnostic observation only; intervention not indicated.

A clinical evaluation of an esterified hyaluronic acid matrix on preparing wounds in burn patients for split-thickness skin grafting

MED-2018-DIV31-006

V2.0

CONFIDENTIAL

- **Grade 2:** Moderate; minimal, local or noninvasive intervention indicated; limited ageappropriate instrumental activities of daily living.
- **Grade 3:** Severe or medically significant but not immediately life-threatening; hospitalization or prolongation of hospitalization indicated; disabling; limiting activities of daily living involving self-care.
- **Grade 4:** Life threatening consequences; urgent intervention indicated
- **Grade 5:** Death related to AE

7.4. Relatedness of Adverse Event and Serious Adverse Event

- **Unrelated:** This category applies to those adverse events which, after careful consideration, are clearly and incontrovertibly due to extraneous causes (disease, environment, etc.)
- **Possible:** This category applies to those adverse events for which, after careful medical consideration at the time they are evaluated, a connection with the Investigational Product administration appears unlikely but cannot be ruled out with certainty.
- **Probable:** This category applies to those adverse events which, after careful medical consideration at the time they are evaluated, are felt with a high degree of certainty to be related to the Investigational Product.
- **Definite:** This category applies to those adverse events which, after careful consideration, are clearly and incontrovertibly due to the Investigational Product.

7.5. Expectedness

The site investigator will be responsible for determining whether an AE or SAE is expected or unexpected. An AE will be considered unexpected if the nature, severity, or frequency of the event is not consistent with the risk information previously described for the device.

Expected AEs include a reaction at the wound site following application of the wound device or infection.

7.6. Adverse Event Reporting

AEs will be recorded on the AE form provided separately by Medline Industries, Inc. Changes in the severity of an AE will be documented to allow an assessment of the duration of the event at each level of severity. Changes in severity will necessitate a new AE form to document the new level of severity. AEs characterized as intermittent require documentation of onset and duration of each episode.

Non-serious AEs should be reported to the study sponsor routinely at a cadence negotiated by the site and CRA. Any AE that meets the requirements for IRB reporting should be done so according to the timeline for this per the IRB.

A clinical evaluation of an esterified hyaluronic acid matrix on preparing wounds in burn patients for split-thickness skin grafting

MED-2018-DIV31-006

V2.0

CONFIDENTIAL

7.7. Serious Adverse Event Reporting

The site investigator shall complete an SAE Form provided separately by Medline Industries, Inc. and submit to the study sponsor as soon as possible, but in no event later than 48 hours after the PI first learns of the event. The PI will be responsible for reporting the event to the IRB if applicable per the IRB's reporting requirements. The study sponsor is responsible for conducting an evaluation of the SAE and shall report the results of such evaluation to the FDA, if applicable, and to all reviewing IRBs, if applicable, within 10 working days after the sponsor first receives notice of the event. Thereafter, the sponsor shall submit such additional reports concerning the event as FDA requests.

For questions regarding this process or the event, you may contact your Medline clinical designee or the Medline Director of Clinical Operations:

Name: [name]
[contact]
E-mail: [contact]

8. STATISTICAL CONSIDERATIONS

8.1. Sample Size Determination

This study is a case series meant to evaluate the clinical usage of the device and is not intended to inform any hypothesis testing. Therefore, a sample size of 20 patients was chosen, which is consistent with a case-series.

8.2. Populations for Analyses

An evaluable population will be used for all analyses, with the definition of evaluable depending on the Phase of the study. For Phase I, all patients with an initial visit and a final interim visit resulting in resolution of Phase I will be included. In Phase II, patients with data from any interim visits who also complete Phase II to resolution will be included in analyses for Phase II.

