Description of Study Intervention:	
This is a case series, in which burn patients meeting all of the inclusion criteria and none of the exclusion criteria will receive Hyalomatrix® Wound Device as a matrix for their wound, in conjunction with the standard-of-care for managing these types of wounds. The study will be divided into two phases. Phase I will entail intervention with the Hyalomatrix® Wound Device and will continue until one of the following occurs, (1) sufficient granulation has occurred and the patient can receive an STSG and proceed to Phase II, (2) the patient's physician determines an STSG is no longer necessary, or (3) two applications with the Hyalomatrix® Wound Device occur and no STSG is approved. Phase II will begin following the STSG procedure. In this phase the wound will be monitored and proportion of STSG take will be evaluated, but no application of the Hyalomatrix® Wound Device will take place. This phase will continue for 28 days or if the physician deems the patient no longer needs regular care to monitor the wound, whichever occurs earlier.

Participant Duration:	
Participant duration will begin upon obtaining informed consent and will end when one of the following occurs:
 
(1) The patient completes Phase II,(2) the patient's physician determines an STSG is no longer necessary,(3) the patient is unwilling or clinically inappropriate, per determination by the Investigator, to receive a second application of Hyalomatrix® Wound Device or STSG. The silicone backing should be removed at 21 days but the decision to reapply the Hyalomatrix® Wound Device or schedule the STSG may happen up to three days thereafter,(4) the patient is not ready to receive an STSG after two applications with the Hyalomatrix® Wound Device. The silicone backing should be removed 21 days after the second application of Hyalomatrix® Wound Device but the decision to schedule the STSG may happen up to three days thereafter,,(5) the patient develops an infection of the target wound at any time,(6) the patient needs NPWT of the target wound after application of the Hyalomatrix® Wound Device.

A clinical evaluation of an esterified hyaluronic acid matrix on preparing wounds in burn patients for split-thickness skin grafting

MED-2018-DIV31-006

V2.0

CONFIDENTIAL

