1.2. Schedule of Activities (SOA)

REQUIRED ASSESSMENTS & ACTIVITIES	SCREENING VISIT Day 0	PHASE I: INITIAL VISIT Day 1	PHASE I: ASSESSMENT VISITS Days 7, 14, 21, 28, 35, 42 ^b	PHASE II: ASSESSMENT VISITS Days 7, 14, 21, 28 ^c , post-Phase I completion
Informed consent	X			
Wound assessment for eligibility	X			
Review of medical history to determine eligibility	X			
A1C test ^a	X			
Demographics, comorbidities, wound history & medication(s)		X		
Wound photograph, infection evaluation, & pain assessment		X	X	
Application of Hyalomatrix® Wound Device and secondary dressing		X		
Record analgesic use		X	X	X

Wound assessment for STSG eligibility			X	
Wound photograph and STSG take assessment				X
Adverse event assessment			X-----X	

a Only for diabetic patients who do not have an A1C reading within the past 90 days

A clinical evaluation of an esterified hyaluronic acid matrix on preparing wounds in burn patients for split-thickness skin grafting MED-2018-DIV31-006

CONFIDENTIAL V2.0

11

b Days must be +/- two days within target day. In most cases, Phase I will end by 21 days. In the event Phase I extends beyond 21 days, a second application of the Hyalomatrix® Wound Device will occur c Days must be +/- two days within target day. Phase II may end earlier depending on participants wound progress.

Medline Industries, Inc.

A clinical evaluation of an esterified hyaluronic acid matrix on preparing wounds in burn patients for split-thickness skin grafting MED-2018-DIV31-006

CONFIDENTIAL V2.0

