4.2. End of Study Definition

A patient's participation in the study may end at several critical points:

- The patient completes Phase II.

A clinical evaluation of an esterified hyaluronic acid matrix on preparing wounds in burn patients for split-thickness skin grafting

MED-2018-DIV31-006

V2.0

CONFIDENTIAL

- The patient's physician determines a STSG is no longer necessary.
- The patient is unwilling or clinically inappropriate, per determination by the Investigator, to receive a second application of the device or STSG. The silicone backing should be removed at 21 days but the decision to reapply the device or schedule the STSG may happen up to three days thereafter.
- The patient is not ready to receive a STSG after two applications of the device. The silicone backing should be removed 21 days after the second application of the device but the decision to schedule the STSG may happen up to three days thereafter.
- The patient develops an infection of the target wound at any time.
- The patient needs NPWT of the target wound after application of the device.

The end of the study will coincide with the issuance of a clinical study report that has been approved by Medline's Clinical Affairs Director.

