6.1.2.5. Infection Evaluation

At this visit, as well as all visits and during the continuum of the patient's participation in the study, the wound site will be evaluated for the development of an infection. In the event of a suspected infection, clinical staff will collect a wound culture. Should a patient develop an infection, this will be noted as an expected adverse event (AE) and the participant's participation in the study will be terminated.

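### Section 8.2 restricts every analysis to evaluable patients, so a patient who leaves the study because of infection can drop out of the infection endpoint (1e)

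*Combined protocol and SAP*

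**What the plan says.** Section 8.2 sets one rule for the whole analysis: "An evaluable population will be used for all analyses, with the definition of evaluable depending on the Phase of the study". The two sets are then defined by how a phase ends. "For Phase I, all patients with an initial visit and a final interim visit resulting in resolution of Phase I will be included". For the later phase, "patients with data from any interim visits who also complete Phase II to resolution will be included in analyses for Phase II". No section says what resolution means, and no all-treated or safety set is named.

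The nearest text to a definition is the synopsis (Section 1.1), where Phase I "will continue until one of the following occurs, (1) sufficient granulation has occurred and the patient can receive an STSG"; the other two endings are that a graft is no longer needed, and that two applications have been made without graft approval. Infection is not on that list. It stands in a separate list of reasons why participation ends, in the synopsis and again in Section 4.2: "The patient develops an infection of the target wound at any time". Section 6.1.2.5 has the wound checked for infection at the initial visit, "as well as all visits and during the continuum of the" patient's time in the study. If infection develops, it is recorded as an expected adverse event and the participant's "participation in the study will be terminated".

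Endpoint 1e (Sections 1.1, 3 and 8.3) counts patients whose target-wound infection is confirmed by culture, whenever it occurs. It therefore spans both phases. Neither Section 8.2 nor Section 8.3 says which set is its denominator.

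**The concern.** The event that 1e counts is also a reason for leaving the study, and the analysis sets are defined by how patients finish. An infection can thus remove the patient from the proportion meant to report it. Losing infected patients lowers 1e. Losing uninfected patients who exit early (for negative pressure wound therapy, or because they are unwilling or clinically inappropriate for a second application or graft) raises it. The direction of the net error depends on who exits, so it cannot be read from the reported figure.

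This matters because 1e is the only harm proportion listed in Section 8.3, which plans no adverse-event summary. A reader shown a low value could not tell whether infections were rare or infected patients were left out. The choice of reading would also be made after the data are known, in an open-label study whose final analysis the sponsor oversees (Section 9.2.3).

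**Working it through.** **Inputs from the protocol.** Planned sample size is 20 (Section 8.1), a stated choice with no power calculation, so there is no figure to reproduce. Phase I interim visits start at Day 7 (Section 1.2), with the window "Days must be +/- two days within target day", so the first falls no earlier than 7 - 2 = Day 5.

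**Inputs assumed.** The protocol gives no infection rate and no exit rate. All counts below are illustrations with 20 treated patients.

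**Step 1: who is lost under each reading.**

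| Reading | Infected patients lost from 1e |
|---|---|
| Narrow: only the three listed endings resolve Phase I | Those infected under the first application. An infection under the second arguably meets the third ending and stays. |
| Broad: any exit resolves Phase I | Only those whose participation ends before a first interim visit, about Day 5 |
| 1e uses the Phase I set, infection after grafting | Normally none, since Phase I was already resolved |
| 1e uses the Phase II set, infection after grafting | Those who exit for infection and so do not complete Phase II |

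The broad reading leaves a gap because Section 8.2 still asks for an interim visit, while infection is looked for continuously and the Instructions for Use (Section 11.1) recommend inspecting the wound bed every 3-4 days. No text turns an exit encounter into an interim visit.

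**Step 2: effect of losing infected patients.** With i infections, of which j are lost, the reported value is (i - j)/(20 - j). Intervals are exact (Clopper-Pearson) 95%.

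- All treated, i = 3: 3/20 = 15.0% (3.2 to 37.9).
- One infected patient lost: 2/19 = 10.5% (1.3 to 33.1), a change of 10.5 - 15.0 = -4.5 points. This arises under the broad reading if one infection ends participation before the first interim visit, or under the narrow reading if one of the three occurs under the first application.
- All three lost: 0/17 = 0% (0 to 19.5). This is the extreme. It needs the narrow reading, all three infections under the first application, and no other exits.
- None lost, as under the broad reading with no infection before the first interim visit: 3/20, no change.

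**Step 3: effect of losing uninfected exits.** With m uninfected patients lost and all three infections kept, the value is 3/(20 - m).

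| m | Value | Change (points) |
|---|---|---|
| 1 | 3/19 = 15.8% | +0.8 |
| 2 | 3/18 = 16.7% | +1.7 |
| 3 | 3/17 = 17.6% | +2.6 |
| 4 | 3/16 = 18.75% | +3.75 |

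Four uninfected exits thus shift 1e almost as far upwards as one lost infection shifts it downwards. Both can happen together: one infected and four uninfected patients lost gives 2/15 = 13.3%, a net change of -1.7 points.

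**Step 4: is the question likely to arise?** The chance of at least one infection among 20 is 1 - (1 - p)^20. At assumed rates p of 5%, 10% and 20% it is 64%, 88% and 99%.

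**The case against.** The narrow reading is not the obvious one. It would remove every first-application infection from an endpoint that sets no limit on when the infection occurs, which is unlikely to be intended. The synopsis list also counts a failure (two applications, no graft approved) as an ending of Phase I, so resolution need not mean success; it may mean only that Phase I ended with a known outcome. Under that broad reading the loss is confined to infections that end participation before about Day 5. How many would do so is unknown, since 1e needs a positive culture and no turnaround time is given. Nothing assigns 1e to the Phase II set. Infections are in any case recorded as adverse events, and in 20 patients the denominator can be rebuilt from the records.

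Most of this stands, and it limits the size of the point. It does not remove it. Section 8.2 says all analyses without exception, the term that decides inclusion is undefined, and the broad reading still requires an interim visit. Recording an event does not settle the denominator of the planned proportion.

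A reader might infer something stronger: that the plan excludes infected patients, or that 1e would be reported as zero. The documents do not support either. Exclusion is possible, not prescribed, and 0/17 is reached only under the three conditions in Step 2. Nor do they support the inference that infections go uncollected.

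**Conclusion.** The point holds as a gap in the analysis sets that can bias a planned result. An infected patient can fall out of both numerator and denominator of 1e, and uninfected early exits can fall out of the denominator, which acts in the opposite direction. From an assumed 3/20, the shift is -4.5 points for one infected patient lost and +0.8 to +3.8 points for one to four uninfected patients lost. The exact intervals overlap widely, so the error lies in the point estimate. These sizes rest on assumed counts and on the reading adopted; under the broad reading with no infection before the first interim visit, no infected patient is lost. The study is descriptive and tests no hypothesis (Section 8.1), so power and type I error are not in question. Severity is minor, but the repair is almost free.

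**What to change.** Add to Section 8.2: *All-treated set: every patient with at least one application of the device. Endpoint 1e and any AE or SAE summary use this set, regardless of evaluability.*

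Add to Section 8.3: *Endpoint 1e is reported with an exact 95% confidence interval. Every early exit (infection, NPWT, unwilling or clinically inappropriate) is listed by phase and study day.*

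Leave the evaluable sets for the efficacy endpoints as they are. Widening resolution to cover every exit would bring patients with no approval date into the primary time-to-approval analysis, and patients with no Day 28 graft-take value into endpoint 1d, and each would then need its own handling rule. Endpoint 1e does not depend on that definition once it has its own set.

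The cost is a few sentences and one listing, with no new visits, since infections are already recorded and the listing covers at most 20 patients. The downside is that patients who exit early are followed for less time, so 1e is a crude proportion with unequal follow-up and should be labelled as such. Its interval also stays wide: even 0/20 leaves an upper limit of 16.8%.

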6.2. Phase II – Post-STSG

6.2.1. Interim Visits – Post-STSG Days 7, 14, 21, 28,

Following the completion of the STSG procedure, the patient will attend up to four interim visits to monitor wound healing progress and percent take of the STSG. Also, at Day 7 visit, information relating to the graft procedure will be recorded on the Surgical Procedures CRF provided separately by Medline Industries, Inc. At each visit, a photograph of the wound will be taken and the site investigator will also determine the percentage of STSG take at each visit, which will be based on the clinical judgement. The patient will also rate current pain level (overall and at the target wound) in an identical fashion to Section 6.1.2.3. A patient's participation in Phase II of the study will continue for 28 days post-STSG or until the site investigator determines weekly care is no longer needed. To document wound healing completion, a photograph of the healed wound will be taken. In order to track the participant's overall outcomes, any returns to the operation

A clinical evaluation of an esterified hyaluronic acid matrix on preparing wounds in burn patients for split-thickness skin grafting

MED-2018-DIV31-006

V2.0

CONFIDENTIAL

room to treat the target wound, any additional inpatient stays, and the type of facility the patient goes to at discharge will be captured on the CRFs. The timing of the visit days is approximate, as scheduling challenges may cause the exact visit days to not occur exactly every seven days. However, visits should occur within +/- two days of the original seven-day interval.

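### Section 8.2 ties every analysis to an undefined resolution while infection ends participation, so patients can drop out of endpoint 1e because they were infected, and 1e has no named denominator

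*Combined protocol and SAP*

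**What the plan says.** Section 8.2 opens with a general rule: "An evaluable population will be used for all analyses, with the definition of evaluable depending on the Phase of the study". The two sets follow. "For Phase I, all patients with an initial visit and a final interim visit resulting in resolution of Phase I will be included". For the second phase, patients need data from an interim visit and must be among those "who also complete Phase II to resolution will be included in analyses for Phase II". No all-treated or safety set is defined.

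Resolution is not defined. The nearest text is in section 1.1 (Synopsis), Description of Study Intervention. There, Phase I "will continue until one of the following occurs, (1) sufficient granulation has occurred and the patient can receive an STSG"; the second ending is that a graft is no longer needed; the third is that two applications of the "Wound Device occur and no STSG is approved". On Phase II the same entry says "This phase will continue for 28 days or if the physician deems the patient no longer needs regular care to monitor the wound", and section 6.2.1 agrees: participation "will continue for 28 days post-STSG or until the site investigator determines weekly care is no longer needed". Infection appears in none of these.

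Infection does end participation. Item 5 of Participant Duration in the Synopsis reads "5) the patient develops an infection of the target wound at any time". Section 4.2 repeats it, in a separate bullet from completion of Phase II, and section 6.1.2.5 terminates participation when an infection develops. Participant Duration and section 4.2 also list exits for need of NPWT and for patients unwilling or clinically inappropriate to go on to a second application or a graft.

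Endpoint 1e (sections 1.1, 3 and 8.3) is the proportion of patients with a culture-confirmed infection of the target wound, counted over the whole study. No denominator is stated.

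**The concern.** The event that 1e counts also ends participation, and entry to the only analysis sets depends on how participation ended. On the most natural reading of section 8.2, a patient who leaves with an infection has not brought that phase to resolution and falls outside its set. Having the event then decides whether the patient is counted.

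There is a second gap. Section 8.2 defines sets by phase, but 1e runs across both phases. Two analysts could follow section 8.2 faithfully and report different infection proportions from the same 20 patients. In a descriptive series the estimates are the result, and section 8.3 promises descriptive statistics, with 95% intervals as appropriate, for all endpoints. A proportion whose denominator depends on the analyst cannot be reproduced. Infection is also one of the expected adverse events named in section 7.5, so readers will look for this figure.

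**Working it through.** **No plan figure to reproduce.** Section 8.1 fixes 20 patients by convention, with no assumed rate, power or precision target. The documents give no expected infection rate, so the counts below are assumptions.

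**Inputs**
- N = 20 treated (section 8.1).
- K = confirmed infections among the treated; 4 assumed.
- b = those infected before Phase I has ended, called before grafting here; a = K − b = those infected later.
- m = uninfected patients whose Phase I exit (NPWT, unwilling or clinically inappropriate) is not counted as resolution.
- Intervals are exact (Clopper-Pearson) 95%.

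**Formulas**
- All treated: K/N.
- Infection exit is not resolution, 1e computed in the Phase I set, later infections counted: a/(N − b − m).
- Infection exit is resolution, other exits not: K/(N − m).

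**Every uninfected patient evaluable (m = 0), K = 4**

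| Treatment of infection exits | b | a | Estimate | 95% CI |
|---|---|---|---|---|
| All treated | any | any | 4/20 = 20% | 5.7-43.7% |
| Not resolution, Phase I set | 4 | 0 | 0/(20 − 4) = 0/16 = 0% | 0-20.6% |
| Not resolution, Phase I set | 2 | 2 | 2/(20 − 2) = 2/18 = 11.1% | 1.4-34.7% |
| Not resolution, Phase I set | 0 | 4 | 4/20 = 20% | 5.7-43.7% |
| Counted as resolution | any | any | 4/20 = 20% | 5.7-43.7% |

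The all-treated row is the benchmark and the proposed remedy. It is not a reading of section 8.2.

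**Other exits.** With K = 4, all after grafting, and m = 3, both formulas that depend on m give 4/(20 − 3) = 4/17 = 23.5% (6.8-49.9%). The denominator can therefore move for reasons unrelated to infection, and the estimate can move up as well as down.

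**Will it arise?** P(at least one infection in 20) = 1 − (1 − p)^20. At assumed rates of 5%, 10% and 20% this is 64%, 88% and 99%.

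**Culture.** Section 6.1.2.5 asks for a culture when infection is suspected, then ends participation if an infection develops. It does not say that the culture must be positive. Endpoint 1e requires confirmation. The patients who exit for infection and those with a 1e event may therefore not be the same.

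**The case against.** The strongest reply is that any final visit, including one at which infection is found, resolves the phase. The text allows this, and on that reading no infected patient is lost. A reader who accepts infection exits as resolution would probably accept the NPWT and unwilling exits too, since the documents list them side by side, and the result would be 4/20. But section 8.2 does not say so, and the qualifier about resolution would then exclude almost nobody who has a final visit.

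The second reply is that the consequence is small. This stands in large part. Section 8.1 disclaims hypothesis testing, 1e is secondary, and infections are recorded as adverse events (sections 6.1.2.5, 7.1 and 7.6), so the count can be recovered. However, sections 8.2 and 8.3 give no denominator for adverse events either.

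Four stronger inferences are tempting, and the documents do not support them:
- *The infection rate will be 0% whatever happens.* This needs 1e to be split into phase-specific sets that remove every case, which sits badly with an endpoint counted at any time. A patient infected between graft approval and the graft has also already resolved Phase I and stays in that set.
- *The error is always downward, or 4/17 is an overstatement.* Direction depends on which exits are excluded. The second claim treats 4/20 as the truth, although patients who left early were not followed to the end.
- *Infection exits and 1e events are different patients.* The natural sequence is suspicion, culture, confirmation, exit. The text supports only that they may differ.
- *Infections will be concealed.* They are captured as adverse events and as reasons for ending participation.

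**Conclusion.** The concern holds in this form: section 8.2 can exclude patients from 1e because they had the 1e event, and it names no denominator for an endpoint that spans both phases. With 4 assumed infections among 20 treated and every uninfected patient evaluable, the Phase I set can show anything from 0% to 20%, depending on how many infections precede grafting. If infection exits count as resolution there is no such loss.

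The size rests on assumed counts, and the intervals are wide throughout; the damage is to the point estimate and its denominator. No test, sample size or decision rule depends on 1e. It should be fixed because the plan states a rule that can work against its own endpoint and the correction is cheap, but it does not undermine the study.

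**What to change.** Amend section 8.2 so that the evaluable sets no longer govern every analysis:

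1. Add an all-treated set: every patient in whom the device was placed at least once. Use it for 1e and for the AE and SAE summaries.
2. Count every culture-confirmed target-wound infection as a 1e event, whether or not it ended participation. List exits for infection without culture confirmation separately. Report the proportion with an exact 95% CI.
3. For the other endpoints, the primary included, define resolution for each phase and state whether exits for infection, for NPWT, and for unwilling or clinically inappropriate patients count.

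This costs a few sentences, one more analysis set and one table. Section 6.1.2.5 already calls for infection evaluation at all visits and a culture on suspicion, so no new procedure is needed, and the rule on when participation ends is untouched. There are two downsides. The reported rate may be less favourable than under the present wording. Patients who leave early for other reasons count as uninfected although their follow-up stopped, so each early exit should be listed with its day and reason.
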